8.4.2 Method of Detecting AEs and SAEs

AEs will be collected at each trial visit. In addition, there will be telephone calls at 2 days +/- 1 day after each dose administration, and a paper patient diary that will be handed out to the patient at each dose administration and reviewed before the next dosing (see Table 1 SoA) as well as spontaneous reports at any time and patients should be instructed to promptly report any symptoms and signs of potential drug reactions to allow timely intervention.

Care will be taken not to introduce bias when detecting AEs. Open-ended and non-leading verbal questioning of the patient is the preferred method to inquire about AE occurrences.

8.4.3 Follow-up of AEs and SAEs

After the initial AE/SAE report, the investigator is required to proactively follow each patient at subsequent visits/contacts. All SAEs and AESIs will be followed until resolution, stabilization or is considered chronic, the event is otherwise explained, or the patient is lost to follow-up (as defined in Section 7.4). Further information on follow-up procedures is provided in Appendix 1, Section 12.

8.4.4 Regulatory Reporting Requirements for SAEs

The PI will review each SAE and evaluate the severity according to the CTCAE criteria V5.0 and the causal relationship of the event to the IMP. All SAEs will be recorded from day 1 (after dosing) until the end-of-study visit. Serious AEs occurring after the end-of-study visit and coming to the attention of the PI must be reported only if there is, in the opinion of the PI, reasonable causal relationship with the IMP. The PI is responsible for providing notification to the Sponsor of any SAE, whether deemed IMP-related or not, that a subject experiences during their participation in the study within 24 hours of becoming aware of the event. As a minimum requirement, the initial

Clinical Study: ES2B-C001-S01 EU CT No.: 2024-516333-12-00

report should provide details of the study, site, subject, details of the SAE and associated treatment with study drug, seriousness criteria and causality assessment. Further relevant information, including concomitant medication, medical history, relevant laboratory evaluation and outcome, should be provided as soon as possible. The Sponsor will request clarification of omitted or discrepant information from the initial notification. The PI or an authorized delegate is responsible for delivering the requested information to the Sponsor within 24 hours of the Sponsor's request or as soon as the requested information is available. Initial reports of SAEs must be followed later with detailed descriptions, including clear photocopies of other documents as necessary (e.g., hospital reports, consultant reports, autopsy reports), with the subject's personal identifiers removed. All relevant information obtained by the PI through review of these documents will be recorded and reported to the Sponsor within 24 hours of receipt of the information. Refer to Section 7.5 for stopping rules in case of a SAE related to the IMP.

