4.3 Dose escalation

A DSMB will be appointed to oversee the trial. The composition and responsibilities of the DSMB is described in a dedicated charter, which will include additional instructions for the dose escalation procedure.

The decision to escalate the dose to the next dosing cohort or initiate the expansion part will be taken by the sponsor based on the DSMB recommendations. For the decision of dose escalation, AEs collected during the DLT period will be assessed by the DSMB. Other available data beyond the DLT evaluation period for all patients in the trial will also be assessed before a decision on escalation to the next dose level can be taken. Dose escalation rules will be based on the number of patients with AEs, specifically DLTs (Section 4.3.2). The DSMB will base recommendations on an evaluation of accumulated safety data and may include other available data, including data on immunogenicity (antibody titers) in their review.

Patients who discontinue for reasons other than toxicity before having DLT evaluable safety data may be replaced at sponsor's discretion.

A schedule of trial procedures is provided in Section 1.3. The administration of adjuvanted and non-adjuvanted ES2B-C001 is described in Section 6 and the trial assessments are described in Section 8.

The dose escalation will include 3 planned dose level cohorts with adjuvanted ES2B-C001 (Section 6.2).

Enrollment will be fully staggered in each of the populations, meaning that an observation period of 3 weeks plus 24 hours is foreseen before the second patient is dosed in one cohort. Dosing of the next subject in each cohort should not take place until 1 week after the preceding patient has received the first dose. Prior to dosing the second patient, safety and reactogenicity data from the previous patient will be discussed at a pre-dosing call between PI(s), CRO medical monitor, and

Clinical Study: ES2B-C001-S01 EU CT No.: 2024-516333-12-00

Sponsor. At subsequent administrations, pre-dosing calls will be scheduled if safety concerns warrant it. This will ensure an evaluation of safety prior to administration of the next patients.

Any safety concerns, such as potential DLTs and/or events that may meet a criterion for initiation of rescue medication, will be escalated to the DSMB who will review accumulated safety data and may provide recommendations for trial adjustments e.g., applying additional overnight stays for patients.

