4.3.1 Dose escalation rules

Dose escalation to a higher dose will be driven by an evaluation by the DSMB. At the time of DSMB evaluation, the last patient in the current dose level cohort must have received the 2nd dose and must have accumulated safety data for 8 weeks following the first dose. This allows for the DLT evaluation period to include an assessment of a potential delay in dose 2 due to toxicity concerns, as described for DLT number 5 in Section 4.3.2.

If one of the 3 patients in a dosing cohort experiences a DLT, 3 additional patients are added to the same dose level cohort. If 2 or more patients among these 6 patients experience DLTs, no further dose escalation can occur, and lower dose levels can be further explored. Dose escalation will continue until not more than 1 out of 6 patients experience DLT in a dose level cohort or the highest dose level group has completed treatment or no trial stopping criterion has been met. See Figure 2.

[figure not shown]

Figure 2: Dose-escalation according to a 3+3 design

Dose escalation will continue until not more than 1 out of 6 patients experiences a DLT in a dose level cohort (see DLT definitions in Section 4.3.2) or the dose level of

Clinical Study: ES2B-C001-S01 EU CT No.: 2024-516333-12-00

treatment has been completed (maximum administered dose MAD) or a trial stopping criterion has been met. The stopping criteria for dose escalation and trial are provided in Section 7.

Patients experiencing DLT will have their administration of adjuvanted or non-adjuvanted ES2B-C001 discontinued. These patients are allowed to remain in the trial to follow safety, disease progression and immune response. The DSMB will convene and recommend whether a re-start of these patients' treatment is advised and if a dose reduction may be required.

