4.3.2 Definition of Dose-limiting Toxicity (DLT)

A DLT is defined as any grade \geq 3 AE according to the NCI-CTCAE v. 5.0 observed at any time from the first administration of ES2B-C001 (alone or adjuvanted) to the 8 weeks thereafter, which despite standard supportive care and in the opinion of the Investigator, is possibly, probably, or definitely related to adjuvanted or non-adjuvanted ES2B-C001, or other event as described below. Investigators evaluation of relatedness to trial treatment administration should take concomitant medication into account.

DLTs will include:

- 1. Any grade ≥ 3 adverse events except:
 - a. Grade ≥ 3 nausea, vomiting, or diarrhea lasting ≤ 72hours with optimal medical therapy Grade 3 fatigue or anorexia lasting < 7 days.
 - b. Fever that occurs within 48 hours of IMP administration and resolves to Grade 2 within 48 hours and is fully resolved within 7 days.
 - c. Non-clinically relevant isolated biochemical abnormalities (e.g., isolated increase in gamma-glutamyltransferase [GGT]).
 - d. Laboratory values out of normal range without related clinical symptoms, clinically transient isolated in nature.
 - e. Laboratory abnormality that is asymptomatic and deemed by the Investigator not to be clinically significant.
- 2. Grade 3 autoimmune reactions, except Grade 3 autoimmune thyroiditis or other endocrine abnormality that can be managed by endocrine therapy.
- 3. Intolerable or > grade 3 injection-site reactions according to FDA guidance 2007 (table 16 appendix 2).
- 4. Grade 2 decrease in left ventricular ejection fraction (LVEF).
- 5. Treatment delay of >14 days due to any related adverse event(s).

In any case, the reported toxicity should be discussed between the Investigators and both the DSMB and the Sponsor. All toxicities will be graded using NCI-CTCAE Version 5.0 based on investigator assessment.

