7.5 Criteria for Temporarily Delaying Enrollment in the Trial and Stopping Rules

Enrollment of new patients in the trial will be temporarily halted if 2 or more out of 6 patients experience DLTs in the same dosing group (as per Section 4.3.2).

In these cases, DLT level has been reached and enrollment at that dose level cannot continue if DLTs are confirmed. The DSMB will review all available, accumulated safety data and recommend further course of action and potentially identify intermediate lower doses for further testing.

The trial includes following trial stopping criterion:

- DSMB recommendation based on patients' medical data and intolerable toxicities.
- Decision from the sponsor to terminate the trial.

8 Trial Assessments and Procedures

For timing of assessments and procedures, refer to the SoA presented in Table 1 (Section 1.3).

Clinical Study: ES2B-C001-S01 EU CT No.: 2024-516333-12-00

In the event of a significant trial-continuity issue (e.g., caused by a pandemic), alternate strategies for patient visits, assessments, medication distribution and monitoring may be implemented by the sponsor or the investigator, as per international, national or local health authority/ethics requirements.

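### Section 8.4.4 relies on Section 7.5 for a related-SAE stopping rule that 7.5 does not contain, so one related fatal or life-threatening event leads to review but to no required hold

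*Protocol*

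**What the plan says.** Section 8.4.4 of the Protocol closes its SAE reporting text with "Refer to Section 7.5 for stopping rules in case of a SAE related to the IMP". Section 4.3.1 likewise places the stopping criteria for escalation and for the trial in Section 7.

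Section 7.5 contains three things:
- A defined trigger: "Enrollment of new patients in the trial will be temporarily halted if 2 or more out of 6 patients" in the same dosing group have DLTs.
- A trial stopping criterion resting on a DSMB recommendation that draws on patients' "medical data and intolerable toxicities".
- A trial stopping criterion resting on a sponsor decision.

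Oversight is spread over other sections. Section 4.3 sends safety concerns to the DSMB, and Section 10.7 repeats this for the whole trial. Section 4.3.2 adds: "In any case, the reported toxicity should be discussed between the Investigators and both the DSMB and the Sponsor". On the affected patient, Section 4.3.1 says "Patients experiencing DLT will have their administration of adjuvanted or non-adjuvanted ES2B-C001 discontinued". On later dosing, Section 4.3 says "At subsequent administrations, pre-dosing calls will be scheduled if safety concerns warrant it", and describes this as the means of evaluating safety before the next patients are treated. Section 4.3 also has data from beyond the DLT window assessed before any escalation.

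**The concern.** The SAE section depends on a rule that is absent from the section it names. Section 7.5 reads as complete sentences and a complete two-item list, with no visible gap where an SAE rule could have been removed.

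This is a first-in-human trial of a self-antigen vaccine, and Section 2.3 describes its clinical safety profile as unknown. After a single related death or life-threatening event, the protocol does not settle whether the next patient may be enrolled at that dose, or whether patients in mid-series receive their next injection, before the DSMB has finished. Those decisions are left to judgement at a moment when a pre-written rule is most useful.

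**Working it through.** **Step 1. What each section imposes after one related fatal or life-threatening event**

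| Section | Action | Who is held |
|---|---|---|
| 8.4.1, 8.4.4 | Report to the sponsor within 24 hours | Nobody |
| 4.3, 10.7 | Escalation to the DSMB, which reviews and may recommend changes | Nobody until it recommends |
| 4.3 | Pre-dosing call before patient 2; later calls if concerns warrant | No hold pending DSMB review |
| 4.3 | Data beyond the DLT window assessed before escalation | The next dose level only |
| 4.3.1 | DLT patient's dosing stops; DSMB convenes on restarting that patient | The affected patient |
| 4.3.2 | Discussion between Investigators, DSMB and Sponsor | Nobody |
| 7.1 | Treating physician may refrain from dosing | Discretionary, patient by patient |
| 7.2 | Pause for cardiac dysfunction or immune disorder | The affected patient |
| 7.5 | Halt at 2 or more of 6 with DLTs | New enrollment, once two patients are affected |
| 10.1 | Immediate-hazard changes need no prior approval | Nobody; this is a permission |

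No row makes new enrollment at the current dose, or other patients' dosing, wait for the review.

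**Step 2. How one event counts toward the 7.5 trigger**

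Inputs: threshold of 2 DLT patients (7.5); DLT window from first dose "to the 8 weeks thereafter" (4.3.2); dose 5 at week 12, plus or minus 7 days (8.3.5.2); End of Study visit at week 18 (8.3.5.1).
- Related death in weeks 0 to 8: 1 DLT patient, and 1 < 2, so no halt. If it is the only DLT among 3 patients, 4.3.1 adds 3 more at the same dose, with no exception for grade 4 or 5.
- Related death after week 8: contributes 0.
- Nominal follow-up outside the window: 18 − 8 = 10 of 18 weeks. Dose 5 falls 12 − 8 = 4 weeks after the window closes, so no event that follows it can count.

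**Step 3. Whether the halt follows later**

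The protocol gives no readable DLT or related-SAE rate, so the rates here are assumptions. Given exactly one DLT in the first 3 patients, the halt is never reached in the cohort of 6 if the next 3 have none, with probability (1 − p)³:
- p = 5%: 0.95³ = 86%
- p = 10%: 0.90³ = 73%
- p = 20%: 0.80³ = 51%
- p = 33%: 0.67³ = 30%

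These figures show only that the DLT count is not a substitute for a rule on severe events. They are not estimates for this vaccine.

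**Step 4. How much the pre-escalation review already covers**

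Take the minimum stagger in 4.3: 3 weeks plus 24 hours (22 days) before patient 2. After that, the next first dose "should not take place until 1 week after the preceding patient has received the first dose". The synopsis words this one-week gap only as an ideal.
- First doses: day 1; 1 + 22 = day 23; 23 + 7 = day 30.
- DLT windows close 56 days later: days 57, 79 and 86. The earliest escalation review is therefore day 86.
- Nominal dose 5, 84 days after first dose: days 85, 107 and 114.

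Patient 1's late period, days 57 to 85, ends before the next dose level can open. For patients 2 and 3, dose 5 falls 107 − 86 = 21 and 114 − 86 = 28 days after the earliest review, when the next cohort may already be enrolling.

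**The case against.** The strongest reply is that the cross-reference is loose but not empty. A related death fits within the DSMB stopping criterion in 7.5, so a stop is available, and what is missing is only an automatic trigger. The surrounding oversight is also substantial: escalation runs through the whole trial, the DSMB convenes after a DLT, concern-driven calls are meant to evaluate safety before the next patients, and late data are assessed before escalation. All of that stands. The late-data review narrows the post-week-8 gap to later events in patients 2 and 3, expansion or backfill patients, slower accrual, and the ongoing dosing of others.

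Section 4.3 also makes opening the expansion part a sponsor decision on DSMB advice. It could be argued that the extra 3 patients are gated in the same way. Section 4.3.1 does not say so, and patients 2 and 3 of a cohort are enrolled before any such decision.

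The DSMB charter and the safety management plan are not shown and may contain a pause rule. That limits how certain one can be about practice. It does not repair the text, because 8.4.4 points to 7.5 and 4.3.1 points to Section 7.

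Two stronger readings are tempting and should not be drawn. A reader might infer that a related death would go unreviewed, or that late events are ignored; Sections 4.3, 4.3.2 and 10.7 rule that out. A reader might also turn the one-week gap into a fixed number of days for deciding on a hold. The protocol states no review deadline or event timing. At a single site, the team that learns of the event is also the team that doses the next patient and may refrain from doing so, so no such figure can be supported.

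**Conclusion.** The point holds as a defect in the stopping rules. Section 7.5 does not contain the related-SAE rule that 8.4.4 relies on, and no readable text requires enrollment at the current dose or other patients' dosing to wait for DSMB review after one related fatal or life-threatening event. Measured against the only defined trigger, such an event counts as 1 of 2 within 8 weeks and 0 of 2 afterwards. In the first case, if it is the only DLT among 3 patients, the written next step is 3 more patients at the same dose.

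No probability of harm is claimed, because the document gives no event rate. The conclusion assumes that the event is judged related, that within the window it is not covered by one of the DLT exceptions in 4.3.2, and that no unseen document supplies the hold. The sponsor might well pause in practice. The change should be made, but the point does not show that the trial lacks oversight.

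**What to change.** Amend the protocol as follows.
- **Section 7.5:** any related fatal or life-threatening event, from first dose to end of study, temporarily pauses new enrollment (including expansion and backfill) and further dosing until the DSMB has reviewed it and recommended in writing. The reference in 8.4.4 can then stay as it is.
- **Section 4.3.1:** make the addition of 3 patients after one DLT subject to this pause.
- **Sections 4.3.2 and 7.1:** state that a delay caused by such a pause is not DLT criterion 5 for other patients and does not count toward the 28-day treatment delay listed as a reason to consider discontinuation. Without this, a long pause could push unaffected patients toward discontinuation.

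The cost is wording in the protocol and the DSMB charter. The downside is a possible short enrollment delay and late doses for patients in mid-series.

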8.4.5 Suspected Unexpected Serious Adverse Reaction (SUSAR) Reporting

Information on SUSARs will be collected and reported to the regulatory authority and the IEC in accordance with European Commission Guidance 2011/C 172/01 ("CT3"), or as per national regulatory requirements in the participating country. This process will be described in detail in the Safety Monitoring Plan (SMP). If the SUSAR is fatal or life-threatening, associated with the use of the IMP, and unexpected, the regulatory authority and the IEC will be notified within 7 calendar days after being made aware of the case. Additional follow-up (cause of death, autopsy report, hospital report) information should be reported within an additional 8 days (15 days in total). SUSARs which are not fatal and nor life-threatening are to be notified within 15 days. Follow-up information may be submitted if necessary. The Sponsor will also provide annual safety reports for submission to the regulatory authority and the IEC responsible for the clinical study. These updates will include information on SUSARs and other relevant safety findings.

SERIOUS ADVERSE EVENT REPORTING INSTRUCTIONS			
Send the SAE Report Form and any supporting documentation via email or fax within 24 hours of becoming aware of the event.			
Contact person for SAE and SUSAR reporting:			

Clinical Study: ES2B-C001-S01 EU CT No.: 2024-516333-12-00

8.4.6 Pregnancy and Postpartum Information

Any female participant who becomes pregnant while participating in the study will discontinue study intervention or will be withdrawn from the study. The PI must follow-up and document the course and the outcome of all pregnancies, including those of female partners of male participants, even if the subject was withdrawn from the clinical study or if the clinical study has finished.

The Investigator will collect pregnancy information on any female participant, or female partner of a male participant, who becomes pregnant while participating in this study. Information will be recorded on the appropriate form and submitted to the Sponsor within 24 hours of learning of a participant's or female partners pregnancy and the pregnant woman will be referred to a physician specialized or experienced in teratology for evaluation and advice. The participant will be followed to determine the outcome of any pregnancy. All outcomes of pregnancy must be reported by the PI to the Sponsor on the pregnancy outcome report form within 24 hours after he/she has gained knowledge of the delivery or elective abortion.

The Investigator will collect any follow-up information on the participant/female partner and the neonate, and the information will be forwarded to the Sponsor. Generally, follow-up will not be required for longer than 6 to 8 weeks beyond the estimated delivery date. Any termination of the pregnancy will be reported, regardless of fetal state (presence or absence of anomalies) or indication for the procedure.

Pregnancy alone is not regarded as an AE unless there is a suspicion that the study drug may have interfered with the effectiveness of a contraceptive medication. Elective abortions without complications should not be regarded as AEs, unless they were therapeutic abortions (see below). While pregnancy itself is not considered to be an AE or SAE, any pregnancy complication or elective termination of a pregnancy will be reported as an AE or SAE. A spontaneous abortion is always considered to be an SAE and will be reported as such. Any post-study pregnancy-related SAE considered reasonably related to study intervention by the Investigator will be reported to the Sponsor. While the Investigator is not obligated to actively seek this information in former study participants, he or she may learn of any pregnancy related information through spontaneous reporting.

Any SAE that occurs during pregnancy must be recorded on the SAE report form (e.g., maternal serious complications, therapeutic abortion, ectopic pregnancy, stillbirth, neonatal death, congenital anomaly, birth defect) and reported within 24 hours in accordance with the procedure for reporting SAEs.

Hospitalization for normal delivery of a healthy newborn should not be considered a SAE.

9 Statistical Considerations

The Statistical Analysis Slan (SAP) will be finalized prior to database lock, and it will include a more technical and detailed description of the statistical analyses described in this section.

Clinical Study: ES2B-C001-S01 EU CT No.: 2024-516333-12-00

9.1 Sample Size Determination

This is a phase I study following a traditional 3+3 design, and no formal statistical hypothesis will be tested. The sample size was estimated to be 9 evaluable patients assuming 3 possible dose levels. However, due to the cohort expansion design, a maximum of 27 evaluable patients in total could be dosed.

